INSTITUTIONAL REVIEW BOARD *at*
KETTERING
HEALTH NETWORK™

RESEARCH PROTOCOL

TO: Kettering Health Network Institutional Review Board

FROM: Principal Investigator: [name]
Phone Number / [contact]
Email Address: [contact]

DATE: 5/29/2017

STUDY TITLE: The Effect of Video Education on Skin-to-Skin at the Time of Delivery

VERSION # 1

1

2 Study Summary

3 The main purpose of this study is to determine the effect of prenatal video education on
4 pregnant women's intention to practice and actual practice of skin to skin contact (SSC)
5 after birth.

6 Purpose

7 This study hypothesizes that education in video format will increase patients knowledge
8 about skin to skin in a way that will make them consider participating in skin to skin
9 immediately after birth. Therefore our end point for this study is intention to participate in
10 SCC measured by a single questionnaire item "Do you plan on participating in skin to skin
11 (or kangaroo care) immediately after birth?" Our secondary end-point will measure whether
12 or not the patient was able to participate in skin to skin within five minutes of delivery.

13 Background and Significance

14 Despite strong support of breastfeeding by organizations such as the American Academy of
15 Pediatrics, the American Congress of Obstetricians and Gynecologists, and the American
16 Academy of Family Physicians, the rate of breastfeeding initiation at the time of delivery and
17 continuation at 6 months postpartum is below the Center of Disease Prevention's Healthy
18 People 2010 goals (1). UNICEF and the World Health Organization (WHO) have estimated
19 that if all babies were breastfed for a minimum of the first six months of their lives, the rate of
20 morbidity and malnutrition would significantly decrease all over the world (2). The benefits
21 of breastfeeding are numerous for both mothers and infants, with infants obtaining optimal
22 nutrition and passive immunity, and mothers obtaining a more rapid return of postpartum
23 uterine tone, postpartum weight loss, delay of ovulation, and decreased risk of breast,
24 ovarian, and endometrial cancers (3). As a result of this information, in 1991 WHO and
25 UNICEF launched the Baby-Friendly Hospital Initiative (BFHI) to encourage proper infant
26 feeding practices starting at birth. It is based on ten steps, which the hospital must meet
27 and maintain to obtain certification. In support of Step Four of the BFHI to "help mothers

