- 133 • Unstable medical status
- 134 • Expecting an unstable baby requiring medical resuscitation
- 135 • Under the age of 18
- 136 • Non-English speaking requiring translation services

137 **Vulnerable Subjects**

138 Pregnant women may be considered vulnerable subjects. Teach back method during the
139 consent process will be used to ensure understanding regarding participation. This study
140 poses no medical risks to pregnant women, fetuses, or neonates. Any pregnant woman
141 appearing to be in a cognitive or emotional state that would prevent informed consent would
142 be excluded.

143 **Research Design and Methods**

144 If participating in the study in the experimental group the patient would watch the video prior to
145 delivery.

146
147 A sample size of 240 (120+120) will participate in this randomized control trial. Alternate
148 patients will be randomized at the time of admission into no video (Group A) and video groups
149 (Group B). 120 patients will be in Group A. 120 patients will be in Group B.

150
151 Randomization will occur in the order that they get enrolled into the study. If an eligible patient
152 wishes to participate in the study, the resident obtaining consent will consult the list of patients
153 to determine if that particular patient will be in Group A or Group B. The first patient enrolled
154 would be in Group A and asked a pre-survey regarding:

- 155 • their intention to practice skin to skin at the time of delivery
- 156 • if they participated in skin to skin in a previous pregnancy
- 157 • if they had any formal education about skin to skin
- 158 • if they did have formal education was it either
 - 159 ○ a.) Provided at a prenatal appointment,
 - 160 ○ b.) A formal class led by either a nurse or a lactation consultant.

161 The second patient enrolled would be in Group B and take the same pre-survey, immediately
162 watch “Jumping into Kangaroo Care”, and then immediately take the post survey which would
163 ask if they intended to practice skin to skin at the time of delivery. The third patient enrolled
164 would take only the pre-survey and be in Group A, etc.

165
166 The video the patients will watch is titled “Jumping into Kangaroo Care” by the Ohio Department
167 of Health. The video is 8 minutes and 52 seconds in length. The video discusses the benefits
168 and logistics of Kangaroo Care from professional’s perspectives and from new mother’s

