169 perspectives. By having patients watch this video before the time of delivery, we can see if
170 patients intend to participate in skin to skin, regardless of their previous education.

171
172 In this study, we will examine patient’s medical record number, age, gestational age, any
173 pregnancy complications, race, type of insurance, and the number of times the patient has been
174 pregnant. We will also examine data that is already collected by this hospital after delivery
175 regarding skin to skin. This includes gestational age in weeks at the time of delivery, 5 minute
176 APGAR, delivery date/time, skin to skin initiation time, skin to skin end time, delivery to skin to
177 skin duration (minutes), and skin to skin duration (minutes). We will also examine if skin to skin
178 is not initiated for patient acuity, maternal acuity, or if the patient refused.

179
180 If a patient has a baby with a 5 minute APGAR less than 7 at the time of delivery or needs to
181 proceed to the operating room for cesarean delivery, the patient would not be included in data
182 collection regarding skin to skin at the time of delivery. For this group, only intention would be
183 measured

184 Surveys / Interviews / Questionnaires

185 Ob/gyn residents at Southview Medical Center will ask the survey questions. The survey will be
186 asked in the patient’s labor room at the hospital once they are admitted. The survey will be
187 administered one-on-one. A copy of the survey has been attached. They will then watch
188 “Jumping into Kangaroo Care” by the Ohio Department of Health if they are in the experimental
189 group. Copyright has been attached.

190 Risks / Discomforts

191 Physical risks or discomforts

192 No known risks

194 Psychological risks or discomforts

195 No known risks

196 Social risks or harms

197 Breach of confidentiality

198 Economic risks

199 No known risks

200 Legal risks

201 No known risks

202 Procedures to Minimize Risks (describe for each risk listed above)

- 203 • Breaches of confidentiality: see *Data Storage and Confidentiality* section

204

205 Specify who will evaluate adverse events / serious adverse events (AEs / SAEs) to identify
 206 and report unanticipated problems: [name], DO

207 **Diagnostic/treatment (non-research) procedures to be used for the study**

208 N/A

209 **Benefits**

210 **Potential benefits to participants**

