 244 Chi-square test of independence will be used to test if significant differences exist between two
 245 groups on quantitative data or on categorical data respectively, at alpha of 0.05, two tailed. Z-
 246 test of two proportions would be used to test if significant differences exist between two groups.

247 Logistic regression would be used in order to account for other variables if necessary. SPSS
248 version 22 will be used to analyze data. [name], associated with Ohio University, will act as our
249 statistician and help us to analyze our data.

250 Data Monitoring to Ensure Safety of Subjects

251

252 Check if this study involves treatment or intervention and provide narrative of plan to
253 monitor data to ensure safety of subjects below:

254 The video intervention involves minimal risk.

255 Privacy Protections

256 We will collect coded data to ensure patient's privacy. We will also recruit and consent in
257 patient's private rooms on labor and delivery.

258 Data Storage and Confidentiality

259 Check all of the following which will be used to access (review), collect, receive, and/or
260 transmit study information:

- 261 **Email** **Camera/Camera Phone** **Portable media (flash drive, CD/DVD, hard drive, etc.)**
262 **Laptop** **Wireless Device** **Internet data access/data entry**
263 **Paper** **KHN Workstation** **Non-KHN computer**
264 **Other (specify):** [Click here to enter text.](#)

265 Describe where data/ records/ samples will be stored and how they will be kept secure:
266 Data will be stored in two binders on labor and delivery at the resident work station. Only
267 approved ob/gyn residents will have access to the study binders. One binder will have the
268 patient's name and enumber along with a number assigned to each patient. The other
269 binder will have the surveys with each survey having the number assigned to each patient.

270
271 Any email communication with PHI will be KHN only. If outside KHN email is needed it will
272 be encrypted. Internet data access will be through Epic. All electronic records will be stored
273 on the resident KHN workstation on L&D that is password protected and only accessible by
274 the PI.

275 Specify who will have access to study information/ to whom it will be released (if applicable):
276 Ob/gyn residents approved to participate in this study will have access to the study
277 information as they will help with the data collection

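### The intention endpoint is asked one-on-one by residents, and only Group B is asked again straight after the film, which adds a pressure to say yes in that group alone

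*Combined protocol and SAP*

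**What the plan says.** The Purpose section makes the primary endpoint a single questionnaire item on intention to take part in SSC immediately after birth. The secondary endpoint is whether SSC took place within five minutes of delivery.

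The Surveys / Interviews / Questionnaires section states that "Ob/gyn residents at Southview Medical Center will ask the survey questions", in the labor room, and that the survey is "administered one-on-one. A copy of the survey has been attached". The attached form is not among the documents available, so its layout and response options are not known here.

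Research Design and Methods shows that allocation is known to the person enrolling. If an eligible woman "wishes to participate in the study, the resident obtaining consent will consult the list of patients", and the groups alternate A, B, A, B. Group A takes the pre-survey only. Group B takes the same pre-survey, watches the film, "and then immediately take the post survey which would" ask about intention again.

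Under Data Storage and Confidentiality, one binder links names to study numbers and the other "binder will have the surveys with each survey having the number assigned to each patient". Both are kept at the resident work station, and approved residents have access to them. The documents describe no masking of the interviewer, no independent interviewer and no private or self-completed answer.

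**The concern.** The endpoint is subjective and is given to a member of the clinical staff. In Group B the question comes directly after the study has presented the case for SSC, and the asker knows this, because only that group has a post-survey. Some women may agree out of politeness without any change in what they intend.

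Such answers add to any real effect of the film and have the same sign. The logistic regression mentioned in Data Analysis cannot take them out, because exposure to this pressure coincides exactly with being in Group B. At stake are the primary test and the decision at the interim look, both of which the plan frames in terms of intention levels.

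**Working it through.** **Inputs.** From Data Analysis: 50% against 80%, two-sided alpha 0.05, 90% power, about 53 per arm; looks at 60 and 120 per group with cut-offs z = 3.5 and z = 2.0. From Research Design and Methods: 120 per group. The share of Group B *no* answers that would change out of courtesy is not in the documents; call it c and treat it as an assumption.

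**The plan's own figure.** For the pooled z test, n = [1.96 × √(2 × 0.65 × 0.35) + 1.2816 × √(0.50 × 0.50 + 0.80 × 0.20)]² / 0.30² = (1.322 + 0.821)² / 0.09 = 51.0, rounded up to 52 per arm. The plan says about 53, so its planning figure is reproduced to within one patient.

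**How many changed answers cross the final cut-off with no true effect?** Treat the item as yes/no and use z = (p_B − p_A) / √[p(1 − p) × 2/120], with p the pooled proportion.

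- Group A at 50% (60 of 120, the planning value):
  - 72 *yes* in Group B: 0.100 / √(0.55 × 0.45 × 2/120) = 1.56
  - 75 *yes*: 0.125 / √(0.5625 × 0.4375 × 2/120) = 1.95
  - 76 *yes*: 0.1333 / √(0.5667 × 0.4333 × 2/120) = 2.08
  - The smallest count that crosses 2.0 is 76, which is 16 of the 60 who would otherwise say no (27%).
- Group A at 80% (96 of 120, an assumption):
  - 107 *yes* in Group B: 0.0917 / √(0.8458 × 0.1542 × 2/120) = 1.97
  - 108 *yes*: 0.100 / √(0.85 × 0.15 × 2/120) = 2.17
  - The smallest count is 108, which is 12 of the remaining 24 (50%).

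Data Analysis gives z = 2.20 for a 10-point difference with 240 women. That value is obtained with 240 per group; 50% against 60% with 120 per group gives the 1.56 above. The discrepancy is a separate matter, but it explains why the two figures differ.

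**Effect on the false-positive rate.** Simulation of the two-look design, 400,000 trials per row, no true effect, p_A = 0.50 and p_B = 0.50 + 0.50c, two-sided cut-offs:

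| Assumed c | p_B | Crosses 3.5 at first look | Null rejected at either look |
|---|---|---|---|
| 0% | 0.50 | 0.03% | 4.6% |
| 10% | 0.55 | 0.1% | 11% |
| 20% | 0.60 | 0.7% | 32% |
| 30% | 0.65 | 3.1% | 64% |
| 40% | 0.70 | 10.1% | 88% |

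The table shows how sensitive the test is to c. It does not estimate c.

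**The case against.** **Who asks.** A reader might infer that the same resident plays the film and then asks the question. No section says so. The survey section describes the survey first and the film afterwards, and Research Design and Methods says only that Group B takes the post-survey. That residents ask it in person is an inference from the general statement that they ask the survey questions, which carries no exception. The inference is reasonable, and the point does not need the same person: whoever asks a post-survey knows that the woman has seen the film.

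**Which group.** A reader might also infer that courtesy answers arise only in Group B. They do not. Group A answers the same item to a resident, after consenting to a study of video education on SSC. Only the increment after the film differs between groups.

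**Size.** Nothing in the documents sizes this increment, so they do not support a claim that the trial would be positive because of it. The 50% base comes from recorded compliance with SSC, not from stated intention. If intention in Group A is much higher, a larger share of the remaining *no* answers has to change. A 10-point shift from 50% does not by itself reach 2.0.

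**A check already in the plan.** SSC within five minutes of delivery comes from data the hospital already collects, which also record refusals. It is less exposed, and a rise in intention with no rise in recorded SSC would be a warning sign. It does not correct the primary estimate, and it is not available to rescue a stopping decision based on intention.

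**Re-asking Group A.** It can be argued that a second survey in Group A would settle the matter. It would equalise the number and timing of questions, which is a real and separate gap. Group A would still not be answering straight after an endorsement of SSC.

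**Conclusion.** The concern holds in limited form. The plan has residents ask a subjective primary endpoint in person, with allocation known, and asks it again only in Group B directly after the film. The resulting increment favors the video and cannot be separated from its effect by analysis of the primary endpoint.

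Its magnitude is unknown. Under the planning base of 50%, roughly one in four of the remaining *no* answers would have to change for a false-positive final test; under an assumed base of 80%, half would. Even so, at the 50% base an assumed change in 10% to 20% of those answers raises the chance of a false-positive trial from about 4.6% to between 11% and 32%. These figures assume a yes/no item, 120 per group and no true effect. The change is worth making before recruitment because nothing in the analysis can undo the bias once the answers have been spoken.

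**What to change.** Revise the Surveys / Interviews / Questionnaires section so that:

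- the woman marks the intention item herself on the numbered paper survey and seals it in an envelope;
- the resident may read the item aloud but does not see or record the answer;
- envelopes stay sealed until data entry, and women are told so before they answer;
- the procedure is identical in both groups and at every survey.

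Sealing matters because residents have access to both binders, so a form simply handed back would not be private from them. The study number already on each survey keeps the link to the patient.

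The cost is envelopes, one revised paragraph and a short instruction to residents. There will be occasional blank or unclear marks, and women with limited literacy will need the item read to them. The change reduces the bias but does not eliminate it, and it does not replace a second intention measurement in Group A.

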211 Participants may benefit by learning the benefits of skin to skin care after delivery.

212 **Potential benefits to others / contributions to knowledge**

213 Others can benefit by learning if video education video education can positively contribute to
 214 patients intent and compliance with skin to skin at the time of delivery

215 **Data Analysis**

216 Preliminary data on both primiparous and multiparous women from our records indicate that
 217 compliance with skin-to-skin is about 50%. We hypothesize that a 30% improvement in intention
 218 along with compliance with SCC is attainable with video education. We also have the ability to
 219 recruit 120 eligible women per group (240 in total) into the study. Using z test for two
 220 proportions, 90% power with alpha of 0.05, two-tailed, we will need about 53 patients per arm
 221 (106 in total) based on assumption that 50% of no formal education group and 80% of video
 222 education group would indicate their intention to participate, and hopefully participate in SCC
 223 post intervention.

224
 225 We will employ interim analysis, based on potentially recruiting 240 patients, and adopt “two
 226 looks”; one at the time when 120 (60 per group) women would be recruited and the other when
 227 240 (120 per group) women would be recruited. We will use cut-off points of $z=3.5$ for first look
 228 and $z=2.0$ for second look, as suggested by O’Brien-Fleming (1979), as decision rules to stop or
 229 continue data collection. If calculated z statistics is greater than 3.5 during first interim analysis,
 230 we will stop data collection. If calculated z-statistics is less than 3.5, we will continue data
 231 collection and reject the null during final analysis only when calculated z-statistics is greater
 232 than 2.0.

233
 234 Assuming 50% and 80% intention levels (30% difference in proportion) during first interim
 235 analysis, 50% interim sample size (120 patients) would result in absolute z- statistics of 4.89 to
 236 stop data collection.

237
 238 If data collection continues due to proportion difference less than 30%, sample size of 240
 239 during final analysis would produce absolute z-statistics of 2.20 to reject the null hypothesis
 240 based on assumption of 10% difference in end-point.

241
 242 Mean (Standard deviation) and sample size (percentage) will be used to summarize normally
 243 distributed continuous data and categorical data respectively. Either t-test of independence or

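### The first-look cut-off of z = 3.5 is not the two-look O'Brien-Fleming value (2.80), and the plan's 50% vs 80% example gives a pooled z of 3.45, not 4.89, so it would not stop the trial

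*Combined protocol and SAP*

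**What the plan says.** All the relevant text is in the Data Analysis section of the combined protocol and SAP.

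- Timing: two looks, "one at the time when 120 (60 per group) women would be recruited and the other when" 240 (120 per group) have been recruited.
- Cut-offs: "We will use cut-off points of $z=3.5$ for first look" "and $z=2.0$ for second look, as suggested by O’Brien-Fleming (1979), as decision rules to stop or" continue.
- Action: "If calculated z statistics is greater than 3.5 during first interim analysis", data collection stops. Otherwise it continues, and the null hypothesis is rejected at the end only if z exceeds 2.0.
- Worked example: "Assuming 50% and 80% intention levels (30% difference in proportion) during first interim" "analysis, 50% interim sample size (120 patients) would result in absolute z- statistics of 4.89 to" stop data collection.
- Error rate: two-sided alpha of 0.05, stated with the sample size and again for the group comparisons ("at alpha of 0.05, two tailed"). The tests named are the chi-square test and the z-test of two proportions. The variance used in the z-test (pooled or unpooled) is not stated.

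**The concern.** The number of looks, their spacing and the alpha level fix the O'Brien-Fleming boundary completely, so the stated cut-offs can be checked against the method cited for them. A first-look value of 3.5 looks too high for two looks. The worked z of 4.89 looks too large for 60 women per group.

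The two points bear on each other. The example is there to show that the effect the trial was designed around would end recruitment at the first look. If the true z lies near 3.5 rather than near 4.9, that reassurance is lost. The decision at the design effect would then turn on a detail of the test that the plan leaves open. Settling that detail after seeing interim data would expose the trial to the charge that the choice was data-driven.

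**Working it through.** **Inputs, all from Data Analysis:** two looks at 60 and 120 per group (information fractions 0.5 and 1); two-sided alpha 0.05; cut-offs 3.5 and 2.0; example rates 50% and 80%; stated interim z 4.89.

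**1. The plan's interim z.** With n per group and mean rate p̄ = (0.50 + 0.80)/2 = 0.65:

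- Pooled, n = 60: z = 0.30 / √(0.65 × 0.35 × 2/60) = 0.30 / 0.0871 = **3.445**
- Unpooled, n = 60: z = 0.30 / √((0.25 + 0.16)/60) = 0.30 / 0.0827 = **3.629**
- Continuity-corrected pooled, n = 60: 3.254; arcsine, n = 60: 3.525
- Pooled, n = 120 per group: z = 0.30 / √(0.65 × 0.35 × 2/120) = 0.30 / 0.0616 = **4.872**

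No version gives 4.89 at 60 per group. The nearest match is the pooled z with the interim total of 120 entered as the size of each group.

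**2. The boundary.** Under the null hypothesis the two z statistics are bivariate normal with correlation √0.5. O'Brien-Fleming sets the cut-offs at c√2 and c. Solving P(|Z₁| > c√2 or |Z₂| > c) = 0.05 gives c = 1.977, so the pair is **2.797 and 1.977**. The Lan-DeMets spending version of the same shape gives 2.963 and 1.969. Neither is near 3.5. The stated pair does resemble the first and last values of a three-look design (3.47, 2.45, 2.00), but the documents do not give that as its source.

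**3. The example against each cut-off.**

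| | z | 3.5 | 2.80 |
|---|---|---|---|
| pooled | 3.445 | continue | stop |
| unpooled | 3.629 | stop | stop |

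With 30/60 controls intending skin-to-skin contact, a pooled-z stop needs 49/60 in the video group with 3.5 (48/60 gives 3.445, 49/60 gives 3.657). With 2.80 it needs 45/60 (44/60 gives 2.629, 45/60 gives 2.828).

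**4. Operating characteristics.** The alpha rows use the normal approximation. The other rows are exact binomial with pooled z unless marked.

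| | 3.5 / 2.0 | 2.80 / 1.98 |
|---|---|---|
| First-look two-sided alpha | 0.0005 | 0.0051 |
| Overall two-sided alpha | 0.0456 | 0.0497 |
| P(stop at 120), 50% vs 80% | 0.486 | 0.762 |
| Same, unpooled | 0.557 | 0.781 |
| Expected enrolment, 240 − 120 × P(stop) | 181.7 | 148.6 |
| Power, 50% vs 80% | 0.9987 | 0.9988 |
| Power, 50% vs 70% | 0.880 | 0.886 |

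With 3.5 kept at the first look, a final cut-off of 1.961 would use the full 0.05.

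**5. The companion figure.** The plan says that a 10-point difference at 240 women gives z = 2.20. It gives no base rate. Taking its own control assumption, 50% vs 60%, the pooled z is 0.10 / √(0.55 × 0.45 × 2/120) = 1.557 at 120 per group. It is 2.202 only at 240 per group. Other base rates give other values at 120 per group: 1.79 for 70% vs 80%, 2.17 for 80% vs 90%, 2.58 for 85% vs 95%. At the plan's control rate the figure shows the same total-for-group slip, and 1.56 would not reject.

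**The case against.** The strongest reply is that nothing false can come of this. A pre-specified first look that is too strict does not inflate type I error, and power hardly moves. The protocol says the site can recruit 240 women and that the video carries minimal risk, and continuing gives more data on the secondary endpoint. How hard it should be to stop early is partly a design preference. All of that stands, and it limits the weight of the point. It does not make 3.5 the value of the cited method, or make 4.89 right.

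Second, the statement that the example does not stop depends on pooling. The unpooled (3.63) and arcsine (3.53) versions both pass 3.5. Pooled is the usual form for this test, and its square is the uncorrected chi-square statistic. But the plan lists the z-test and the chi-square test separately, so reading it as pooled is an inference. This also stands. What holds without condition is that 4.89 is wrong in every version checked, and that the plan leaves the decision at its own design effect undetermined.

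Third, 2.80/1.98 is not free of cost. Its exact type I error is 0.047, 0.051 and 0.049 at common rates of 50%, 65% and 80%, so it very slightly exceeds 0.05 at 65%, the pooled rate of the plan's example. The existing pair stays below 0.05 at all three rates. The excess is trivial but should be known.

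**Conclusion.** The point holds. For the design as written, the first-look cut-off attributed to O'Brien-Fleming should be 2.80, not 3.5; the final 2.0 is correct to rounding. The worked interim z should be about 3.45 pooled (3.63 unpooled), not 4.89, and with the pooled z the plan's claim that its assumed effect stops the trial fails.

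The consequence is for efficiency and clarity, not validity. At true rates of 50% and 80%, the stated cut-off lowers the chance of stopping at 120 women from 76% to 49% and adds about 33 women to expected enrolment (181.7 − 148.6).

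This rests on equal allocation, looks at exactly half and full enrolment, every enrolled woman contributing to the intention endpoint, and, for the exact figures, the pooled z. The boundary values were computed, not taken from the cited paper.

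**What to change.** Make the change before the first look. There are two acceptable routes, both confined to Data Analysis.

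1. **Preferred.** Set the rule to |z| ≥ 2.80 at 120 women and |z| ≥ 1.98 at 240, on the primary intention endpoint. State that z uses the pooled variance. Replace 4.89 with about 3.45, which does exceed 2.80, so the statement that the example stops becomes true.
2. **If a stricter first look is wanted.** Keep 3.5 and 2.0 but remove the O'Brien-Fleming attribution. State the overall alpha of 0.046, or use 1.961 at the end to spend the full 0.05. Name the pooled variance, correct 4.89, and say that an observed 50% vs 80% would continue to 240.

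Under either route, state the base rate behind the final-look example and recompute its z of 2.20.

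The cost is a few numbers and one phrase on the variance, with no new data. The downside of the first route is that more frequent early stopping leaves fewer women for the secondary endpoint when the effect is large.

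### The two planning z-statistics, 4.89 and 2.20, match twice the planned group sizes; the correct values are about 3.45 and 1.56, below the plan's cut-offs of 3.5 and 2.0

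*Combined protocol and SAP*

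**What the plan says.** The comparison is a z test for two proportions, with 50% intention assumed in the control group and 80% in the video group (protocol, Data Analysis). There are two looks: "one at the time when 120 (60 per group) women would be recruited and the other when" all 240 (120 per group) have been recruited. The 120 + 120 split is repeated under Research Design and Methods. The cut-offs are z = 3.5 at the first look and z = 2.0 at the second.

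Two sentences then show how the rule is expected to behave:

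- Interim: "Assuming 50% and 80% intention levels (30% difference in proportion) during first interim" analysis, the "50% interim sample size (120 patients) would result in absolute z- statistics of 4.89 to" stop data collection.
- Final: if the trial continues, a sample of 240 "during final analysis would produce absolute z-statistics of 2.20 to reject the null hypothesis", "based on assumption of 10% difference in end-point". The two rates behind that 10-point difference are not given.

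**The concern.** These sentences are the plan's only illustration of what the stopping rule and the final test can do. The first tells the reader that the hypothesised effect would clear the interim boundary with a wide margin. The second tells the reader that an effect one third as large would still be significant at the end. Both figures look too large for 60 and 120 women per group, by a factor of about √2.

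If they are wrong, the investigators and the review board expect early stopping that is only about as likely as not. They also expect a sensitivity to small effects that the trial lacks. A non-significant result could then be read as evidence against a 10-point benefit when the trial would usually miss such a benefit.

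**Working it through.** **Inputs, all from Data Analysis.** Interim: 60 per group, 50% versus 80%, cut-off 3.5. Final: 120 per group, 10-point difference, cut-off 2.0. For the final look I assume 50% versus 60%, because 50% is the only control rate the plan states.

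**Formula.** Pooled z = d / √(2·p̄·(1 − p̄)/n), where d is the difference, p̄ the mean of the two rates and n the number per group.

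**Reproducing the plan's figures.** Both appear when the total is put in place of n:

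- 50% versus 80%, n = 120: 0.30 / √(2 × 0.65 × 0.35 / 120) = 0.30 / 0.06158 = 4.87 (stated 4.89).
- 50% versus 60%, n = 240: 0.10 / √(2 × 0.55 × 0.45 / 240) = 0.10 / 0.04541 = 2.20 (stated 2.20).

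Solving for n, 4.89 implies about 121 per group and 2.20 about 240 per group.

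**At the actual group sizes:**

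- Interim, n = 60: 0.30 / √(2 × 0.65 × 0.35 / 60) = 0.30 / 0.08708 = 3.445.
- Final, n = 120: 0.10 / √(2 × 0.55 × 0.45 / 120) = 0.10 / 0.06423 = 1.557.

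**Other forms of the test:**

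| Form | Interim, 60 per group | Final, 120 per group |
|---|---|---|
| Pooled | 3.445 | 1.557 |
| Unpooled | 3.629 | 1.565 |
| Arcsine | 3.525 | 1.560 |
| Log-odds | 3.354 | 1.554 |
| Pooled, continuity-corrected | 3.254 | 1.427 |
| Unpooled, continuity-corrected | 3.428 | 1.435 |

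No form gives an interim value above 3.63 or a final value above 1.57.

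**Which form the plan used.** For 90% power at two-sided 0.05, the pooled formula needs 52 per arm, against the plan's stated 53; the unpooled formula gives 48. The square of the pooled z is also the Pearson chi-square statistic, and the plan names a chi-square test. The pooled form is therefore the best reading.

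**Consequences at the interim.** If the true rates are 50% and 80%, the exact binomial chance that z exceeds 3.5 with 60 per group is 0.486 pooled and 0.557 unpooled. A mean z of 4.89 would imply about Φ(4.89 − 3.5) = Φ(1.39) = 0.92.

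**Consequences at the final look, 50% control rate:**

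- The formula reaches z = 2.0 at a difference of about 12.8 points. In whole patients, with 60/120 in the control group, 75/120 gives z = 1.95 and 76/120 (13.3 points) gives 2.08.
- Power over both looks is about 0.32 to 0.33 for a true difference of 10 points, 0.80 for 18 points and 0.91 for 21 points.

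**The case against.** **The interim shortfall depends on the variance form.** The plan names a z test for two proportions but no variance. Pooled 3.445 misses 3.5 by 0.055, while unpooled 3.63 and arcsine 3.53 pass it. With 30/60 in the control group, one more woman in the video group (49/60 instead of 48/60) would lift the pooled z to 3.66. This stands as a limit: the interim value is borderline. It does not rescue 4.89, which no form comes near.

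**The rates behind the 10-point difference are not stated.** With 120 per group, 80% versus 90% gives 2.17 pooled and 2.20 by arcsine, so 2.20 can be reached without doubling n. That is true, but the plan nowhere assumes an 80% control rate, and this reading does not explain 4.89. The 50% versus 60% reading explains both figures with one error. It remains an inference.

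**The cause is not visible.** Using the total as the group size and dropping the factor 2 from the variance are numerically the same. The 0.02 gap between 4.87 and 4.89 looks like rounding. The corrected values do not depend on which it was.

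**The consequences are limited.** The 53 per arm is approximately right, the target of 240 rests on recruitment capacity, and neither cut-off uses the wrong figures. The exact two-look error rate at 50% in both groups is about 4.5%, and power for 50% versus 80% over both looks is about 99.9%. All of this stands. The harm lies in what readers are told about early stopping and about small effects.

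**Conclusion.** The concern holds. Both stated values are too large by about √2 at the group sizes the plan sets. The interim z for 50% versus 80% is 3.45 rather than 4.89, and the final z for 50% versus 60% is 1.56 rather than 2.20. On the pooled test, neither illustrated result crosses its own cut-off.

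The final-look failure is clear under every form of the test, given a 50% control rate. The interim failure is narrow and rests on the pooled variance; under any form, stopping early is roughly an even chance rather than an expectation. The trial remains well powered for its 30-point hypothesis. It is not powered for 10 points, where it would miss a true effect about two times in three. Because these figures describe the decision rule for the primary comparison, they should be corrected before the plan is relied on.

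**What to change.** In Data Analysis:

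1. Replace 4.89 with 3.45, naming the pooled variance and 60 per group. Remove the statement that this result would stop data collection, or say instead that the chance of stopping at the first look is about one half if the true rates are 50% and 80%.
2. Replace 2.20 with 1.56, naming 50% versus 60% and 120 per group. Delete the claim that a 10-point difference rejects the null. If other base rates were meant, state them and recompute.
3. Add that, with 120 per group and a 50% control rate, the smallest observed difference reaching z = 2.0 is about 13 points, and that a true difference of about 18 points is needed for 80% power and about 21 points for 90%.

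This is a change of text only. Enrolment, cut-offs and procedures stay as they are. The cost is that the stated detectable difference becomes less favourable.
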